## 8 Statistical analyses to be used in this study

### 8.1 Disposition of subjects

The number of subjects will be tabulated for the following populations:

- Screened
- Randomised
- Modified ITT
- PP
- Safety
- Discontinued study
- Completed study

The disposition and number and reasons for withdrawal and discontinuations will be listed and, if needed, tabulated by treatment sequence. Reasons for excluding subjects or subject periods from pharmacokinetic analyses will be listed. Data from subjects who failed at screening will be included only in the disposition tabulations and data listings.

### 8.2 Demographic and other baseline characteristics

Demographic and other baseline characteristics will be tabulated by treatment sequence. Medications taken by the subjects before, during, and after the study will be classified by ATC Level 3 and drug name, and will be tabulated and/or listed as appropriate. WHO – DD will be used for coding prior and concomitant medications. No statistical tests will be performed.

### 8.3 Extent of exposure and measurements of treatment compliance

Each study subject will receive the study treatments under observation of the site personnel. The exposure will be verified by measurement of drug concentrations. Any deviation from the planned compliance and exposure will be listed. Drug administration and plasma concentration data will be listed and tabulated by treatment. The number of subjects exposed to study treatments and the number of doses administered will be tabulated by treatments.

### 8.4 Analysis of pharmacokinetic variables

Table 2 lists the PK parameters which will be derived from the concentration-time data of levodopa, carbidopa, 3-OMD and, ODM-104.

Table 2. PK parameters to be calculated for levodopa, carbidopa, 3-OMD and ODM-104.

| Parameter     | Levodopa       | Carbidopa      | 3-OMD          | ODM-104        |
|---------------|----------------|----------------|----------------|----------------|
| $C_{max}$     | X  | X  | X  | X  |
| $C_{max,tau}$ | X  |                |                | X              |

|  |                |                |                |                |
|--|----------------|----------------|----------------|----------------|
| $t_{\max}$                             | X              | X              | X              | X              |
| $t_{\max,\tau}$                        | X              |                |                | X              |
| $C_{\min,\tau}$                        | X  |                |                | X              |
| $C_{\min,\tau,\text{actual}}$          | X  |                |                |                |
| $AUC_{\tau}$                           | X  |                |                | X              |
| $AUC_{0-16}$                           | X  |                |                |                |
| $AUC_{0-24}$                           | X  | X  | X  | X  |
| $AUC_{\infty}$                         | X              |                |                | X              |
| $t_{1/2}$                              | X              |                |                | X              |
| $\lambda_z$                            | X              |                |                | X              |
| $C_{\max}/C_{\min,\tau}$               | X  |                |                |                |
| $C_{\max}/C_{\min,\tau,\text{actual}}$ | X  |                |                |                |
| $C_{\max}/C(16h)$                      | X  |                |                |                |
| $PTF_{\tau}$                           | X  |                |                |                |
| $PTF_{0-16h}$                          | X  |                |                |                |

 Statistical analysis will be performed

#### 8.4.1 Primary PK parameter

The primary PK variable for the evaluation of PK of levodopa is AUC0-24 to describe the total levodopa exposure. The primary PK variable will be summarised using descriptive statistics by treatment and analysed using a mixed linear model with 90% CI applicable for the crossover design. The statistical model will include treatment and period as fixed effects and subject as a random effect. Sensitivity analysis adjusted for subject weight and age will be performed.

The following SAS-code for the primary comparison will be applied:

```
proc mixed data=pkparam2 plots=all alpha=0.10;
  class subject trtpcd visit;
  model log_auc = trtpcd visit / ddfm=KR outp=Resid solution;
  random subject;
  lsmeans trtpcd / diff cl alpha=0.10;
  ods output tests3=testCross lsmeans=lsmeansCross
  diffs=diffscross;
  by group;
run;
```

The following SAS-code for the sensitivity analysis will be applied:

```
proc mixed data=pkparam2 plots=all alpha=0.10;
  class subject trtpcd visit;
  model log_auc = trtpcd visit weightkg age / ddfm=KR outp=Resid
solution;
random subject;
lsmeans trtpcd / diff cl alpha=0.10 adjust=tukey ADJDFE=ROW;
ods output tests3=testCross2 lsmeans=lsmeansCross2
diffs=diffscross2;
by group;
run;
```

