## 5 Statistical hypotheses

The primary variable for the evaluation of PK of levodopa is  $AUC_{0-24}$  to describe the total levodopa exposure. Primary comparison will be made within levodopa dose level groups, between crossover treatment arms levodopa / 12.5, 25 or 37.5 mg of carbidopa and levodopa / 65 mg of carbidopa / 100 mg of ODM-104. I.e. comparisons A1 vs. D1, A2 vs. D2, A3 vs. D3, and A4 vs. D4 will be the primary ones.

Other crossover comparisons will be performed and considered as secondary. Parallel group comparisons may be performed. The conclusions on possible differences between treatments will be based on both overall evaluation of levodopa concentration-time profiles and formal statistical analyses of PK parameters.

$H_0: AUC_{0-24, \text{levodopa/carbidopa / ODM-104}} = AUC_{0-24, \text{levodopa/carbidopa}}$

$H_1: AUC_{0-24, \text{levodopa/carbidopa / ODM-104}} \neq AUC_{0-24, \text{levodopa/carbidopa}}$

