## 7.2 Statistical issues

### 7.2.1 Significance level and confidence intervals

90% confidence intervals and p-values will be produced between different treatments. A two-sided significance level of 10% will be considered the level of statistical significance. Confidence intervals and p-values will be presented up to four decimal places.

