#### **7.2.6 Multiplicity**

For the primary comparisons, there is only one primary comparison in each group, thus multiplicity correction is not needed. For secondary comparisons, where several treatments are included, all pairwise comparisons will be adjusted according to Tukey method.

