##### 14.2 Pharmacokinetic data

|                  |   |
|------------------|---|
| Table 14.2.1.1   | Levodopa concentration (ng/ml)  |
| Table 14.2.1.2.1 | AUC tau (h*ng/mL) of levodopa  |
| Table 14.2.1.2.2 | Statistical analysis for AUC tau of levodopa                           |
| Table 14.2.1.3.1 | AUC 0-24 (h*ng/mL) of levodopa   |
| Table 14.2.1.3.2 | Statistical analysis for AUC 0-24 of levodopa                          |
| Table 14.2.1.4.1 | AUC 0-16 (h*ng/mL) of levodopa   |
| Table 14.2.1.4.2 | Statistical analysis for AUC 0-16 of levodopa                          |
| Table 14.2.1.5   | AUC inf (h*ng/mL) of levodopa  |
| Table 14.2.1.6.1 | C max,tau (ng/mL) of levodopa  |
| Table 14.2.1.6.2 | Statistical analysis for C max,tau of levodopa                         |
| Table 14.2.1.7.1 | C max (ng/ml) of levodopa  |
| Table 14.2.1.7.2 | Statistical analysis for C max of levodopa                             |
| Table 14.2.1.8.1 | C min,tau (ng/mL) of levodopa  |
| Table 14.2.1.8.2 | Statistical analysis for C min,tau (ng/mL) of levodopa                 |
| Table 14.2.1.8.3 | Actual C min,tau (ng/mL) of levodopa                                   |
| Table 14.2.1.8.4 | Statistical analysis for actual C min,tau (ng/mL) of levodopa          |
| Table 14.2.1.9.1 | C max / C min ratio tau of levodopa                         |
| Table 14.2.1.9.2 | Statistical analysis of C max / C min ratio tau of levodopa |

|                   |  |
|-------------------|--|
| Table 14.2.1.9.3  | Actual Cmax / Cmin ratio tau of levodopa                         |
| Table 14.2.1.9.4  | Statistical analysis of actual Cmax / Cmin ratio tau of levodopa |
| Table 14.2.1.10.1 | Cmax / C(16h) of levodopa  |
| Table 14.2.1.10.2 | Statistical analysis of Cmax / C(16h) of levodopa                |
| Table 14.2.1.11   | tmax,tau (h) of levodopa   |
| Table 14.2.1.12   | tmax (h) of levodopa   |
| Table 14.2.1.13   | t1/2 (h) of levodopa   |
| Table 14.2.1.14   | Lambda z of levodopa   |
| Table 14.2.1.15.1 | PTFtau of levodopa   |
| Table 14.2.1.15.2 | Statistical analysis for PTFtau of levodopa                      |
| Table 14.2.1.16.1 | PTF0-16 of levodopa  |
| Table 14.2.1.16.2 | Statistical analysis for PTF0-16 of levodopa                     |

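### The main AUC0-24 code outputs all six treatment pairs unadjusted, although SAP 7.2.6 requires Tukey adjustment for the five secondary pairs

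*SAP*

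**What the plan says.** SAP section 5 names A versus D as the primary comparison in each group and says of the remaining pairs: "Other crossover comparisons will be performed and considered as secondary". SAP 7.2.6 then gives two rules. For the primary contrast, "there is only one primary comparison in each group, thus multiplicity correction is not needed". For secondary comparisons, "all pairwise comparisons will be adjusted according to Tukey method". SAP 7.2.1 sets the threshold: "A two-sided significance level of 10% will be considered the level of statistical significance".

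SAP 8.4.1 gives two blocks of code for AUC0-24:

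- The main model is introduced with "The following SAS-code for the primary comparison will be applied" and contains "lsmeans trtpcd / diff cl alpha=0.10", run by group.
- The sensitivity model adds weight and age and contains "lsmeans trtpcd / diff cl alpha=0.10 adjust=tukey ADJDFE=ROW".

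The list of tables in SAP 10.1 has one statistical table for levodopa AUC0-24, "Table 14.2.1.3.2". The draft page in SAP 10.3 shows the six Group 1 pairs (A1-B1, A1-C1, A1-D1, B1-C1, B1-D1, C1-D1) with one 90% confidence interval column and one p-value column. No pair is marked as primary, secondary, adjusted or unadjusted.

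**The concern.** The code does not deliver the written rule. Without an `adjust=` option, the main-model statement returns unadjusted intervals and p-values for every pair. For AUC0-24, Tukey is coded only in the sensitivity model, where it also adjusts the A-D contrast that 7.2.6 exempts. A programmer who follows 8.4.1 breaches 7.2.6 for five of the six pairs, and one who follows 7.2.6 departs from the code in 8.4.1.

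The secondary pairs carry real weight here. In Groups 1 to 3, A versus D changes carbidopa and ODM-104 together. The separate effects on AUC0-24 come from secondary pairs: A-B for carbidopa, and B-C, B-D and C-D for ODM-104. Protocol section 1.2 says the study is meant to justify the carbidopa and ODM-104 doses for phase III without formal phase II dose-finding studies. Left unadjusted, these pairs would be judged at the 10% level with more false positives than the SAP allows, and a reader of the table could not tell which rule had been applied.

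**Working it through.** **Inputs.** Four treatments per group, 14 subjects randomised per group, 12 used for planning, and a within-subject SD of 0.139 on the log scale (SAP section 6). Two-sided level 0.10 (SAP 7.2.1). Complete data are assumed.

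**The plan's own figures.** The planning difference reproduces: ln(1.40) = 0.336. The stated 80% power at n = 12 does not: these inputs give more than 99.9%. That is a separate and conservative discrepancy, and only the SD is used below.

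**Pairs.** 4 × 3 / 2 = 6 per group: one primary (A-D) and five secondary.

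**Critical values.** Residual df = 3(n − 1) − 3. The SE of a pairwise log difference is 0.139 × √(2/n). The Tukey critical value is the 90th percentile of the studentized range for four means, divided by √2.

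| | n = 14 | n = 12 |
|---|---|---|
| df | 36 | 30 |
| SE | 0.0525 | 0.0567 |
| Unadjusted t | 1.688 | 1.697 |
| Tukey | 2.376 | 2.394 |
| Ratio | 1.41 | 1.41 |
| Half-width, unadjusted | 0.089 | 0.096 |
| Half-width, Tukey | 0.125 | 0.136 |

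**Observed ratios on which the two rules disagree.** At n = 14 the band runs from exp(1.688 × 0.0525) = 1.093 to exp(2.376 × 0.0525) = 1.133, or 0.883 to 0.915 in the other direction. At n = 12 it is 1.101 to 1.146. Fourteen subjects cannot split equally over four sequences. Splits of 4/4/3/3 give a period-adjusted SE of 0.0525 to 0.0528, which moves the n = 14 band to at most 1.093 to 1.134.

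**Familywise error over the truly equal secondary pairs** (simulation, 1,000,000 draws, n = 14):

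| Truth | Unadjusted | Tukey |
|---|---|---|
| A = B and C = D, with D above A | 18.8% | 4.5% |
| B = C = D, with D above A | 22.3% | 5.8% |
| No treatment differs | 31.7% | 8.8% |

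The n = 12 results agree to within 0.2 percentage points.

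**Power for one secondary pair.** The true ratio of 1.10 is chosen for illustration and is not a planning value. The noncentrality is ln(1.10)/0.0525 = 1.81. Power is 55% unadjusted and 30% with Tukey, so the two rules reach different conclusions in 25% of trials. At n = 12 the figures are 50% and 25%.

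**The case against.** The strongest reply is that no rule is contradicted. The code is introduced as being for the primary comparison, and for A-D the absence of adjustment is exactly what 7.2.6 says. `lsmeans / diff` prints every pair by default, and printing a pair is not a plan to report it unadjusted. On this view 7.2.6 governs and only a code snippet is missing. The first part stands: the code is right for A-D. However, no other main-model code produces the five remaining pairs, and the draft table reports them.

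The templates are drafts headed as examples, and only page 1 of 8 of this table is shown. The other pages may hold Tukey results, perhaps from the sensitivity model. That limits the labelling point to the visible page. Nothing in the documents says that Tukey results from the main model appear elsewhere.

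SAP 7.2.6 speaks of adjusting comparisons and does not mention intervals. The SAP's own Tukey code combines `cl` with `adjust=tukey`, which also gives adjusted limits, so applying the rule to the intervals is the natural reading. It is still an inference.

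Reading secondary comparisons as meaning only secondary variables is weak, because section 5 uses the term for the other crossover comparisons of AUC0-24.

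Finally, conclusions also rest on the concentration-time profiles, no secondary pair has a go/no-go threshold, and the adjusted results can be obtained at any time from the same model. These points limit the seriousness but do not remove the mismatch.

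**Conclusion.** The concern holds. Followed as written, the main AUC0-24 code and the visible draft table would report five of the six pairs in each group without the Tukey adjustment that 7.2.6 requires. Intervals for those pairs would be 1.41 times narrower on the log scale than the rule gives.

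The familywise figures of 19% and 22% are the relevant ones, since the trial is planned on D exceeding A by 40% at the 100 mg levodopa strength. The 32% figure applies only if no treatment differs. The ratio bands and power figures rest on the planning SD of 0.139 and complete data; the critical values and error rates do not depend on the SD.

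The primary A-D result, all point estimates and the sample size are unaffected. This should be corrected before results are seen, but it does not threaten the primary conclusion.

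**What to change.** Add `adjust=tukey adjdfe=row` to the `lsmeans` statement of the main AUC0-24 model in SAP 8.4.1. The output then holds unadjusted and adjusted values side by side. State that A-D is reported unadjusted and the other five pairs Tukey-adjusted, for both intervals and p-values, and label the pairs accordingly in Table 14.2.1.3.2. Also state that the weight- and age-adjusted sensitivity analysis follows the same rule, with A-D unadjusted.

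If unadjusted intervals were intended for the secondary AUC0-24 pairs, 7.2.6 should say so and the table should label them as unadjusted. The protocol's statistical section sets no multiplicity rule that would prevent this.

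The cost is one SAS option, a sentence or two and a table footnote. The five secondary intervals become 1.41 times wider on the log scale, as 7.2.6 already implies. The increase detectable with 80% power in a secondary pair rises from 14.2% to 18.5% at n = 14 (log difference 0.133 to 0.170), or from 15.5% to 20.3% at n = 12 (0.144 to 0.185).

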8.4.3 Pharmacokinetic analysis

The primary variable for the evaluation of PK of levodopa is AUC_{0-24} to describe the total levodopa exposure. The secondary PK variable is $C_{min,tau}$, which is used to describe minimum concentration during the dosing intervals. The ratio of the C_{max} in a dosing interval and the observed concentration at the end of the dosing interval, $C_{max}/C_{min,tau}$, which is used to describe levodopa fluctuation during the dosing intervals and other PK variables of levodopa, 3-OMD, carbidopa and ODM-104 will be evaluated as other variables.

PK parameters will be analysed after logarithmic transformation and 90% confidence intervals (CIs) for the geometric means will be calculated.

The conclusions regarding possible differences between different study treatments will be based on both overall evaluation of levodopa concentration-time profiles and formal statistical analyses of PK parameters.

Primary pharmacokinetic evaluation

The primary PK variable will be summarised using descriptive statistics by treatment and analysed using a mixed linear model with 90% CI applicable for the crossover design. The statistical model will include treatment and period as fixed effects and subject as random effect. Sensitivity analysis adjusted for subject weight and age will be performed.

Levodopa fluctuation ratios ($C_{\max}/C_{\min,\tau}$, $C_{\max}/C_{(16\text{ h})}$, PTF_{τ} and PTF_{0-16}), and AUC_{0-24} , C_{\max} and $C_{\min,\tau}$ will be the main PK variables of interest.

The primary conclusions will be based on the PP population.

Secondary pharmacokinetic evaluation

Statistical evaluation for secondary PK variable will be done using similar methods as for primary variable. Statistical model for $C_{\min,\tau}$ will include treatment, period, dosing interval, and treatment by dosing interval interaction as fixed effect and subject by period interaction as random effect.

Other pharmacokinetic evaluations

The other PK variables for the evaluation of PK of levodopa, carbidopa, 3-OMD and ODM-104 are presented in [Table 4](#). All PK variables will be summarised by treatment using descriptive statistics. Selected PK variables will be analysed using similar models and sensitivity analysis to the primary and secondary PK variables. Drug concentrations will be tabulated by time and treatment with descriptive statistics.

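### The weight-and-age sensitivity model says almost nothing about the within-subject A–D contrast, and the Tukey option in its code runs against SAP 7.2.6

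*SAP*

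**What the plan says.** SAP 5 names the primary contrasts: "comparisons A1 vs. D1, A2 vs. D2, A3 vs. D3, and A4 vs. D4 will be the primary ones". Each compares two treatments in the same subjects.

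The primary code in SAP 8.4.1 is run by group with subject random. Its model is "model log_auc = trtpcd visit / ddfm=KR outp=Resid solution", and its LSMEANS line is "lsmeans trtpcd / diff cl alpha=0.10" with no multiplicity option.

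Protocol 8.4.3 commits to a further analysis: "Sensitivity analysis adjusted for subject weight and age will be performed". SAP 8.4.1 implements it as "model log_auc = trtpcd visit weightkg age / ddfm=KR outp=Resid", again by group with subject random, but with a different LSMEANS line: "lsmeans trtpcd / diff cl alpha=0.10 adjust=tukey ADJDFE=ROW".

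On multiplicity, SAP 7.2.6 says of the primary comparisons that "there is only one primary comparison in each group, thus multiplicity correction is not needed", and for secondary comparisons that "all pairwise comparisons will be adjusted according to Tukey method". SAP 5 classes the other crossover comparisons as secondary, so 7.2.6 covers the remaining pairs on AUC0-24.

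Weight is measured at screening and at the end-of-study visit (Protocol Table 3, 6.1.1 and 6.1.3), not in the treatment periods. The template for the AUC0-24 analysis (SAP 10.3, Table 14.2.1.3.2) has one confidence-interval column and one p-value column for all six pairs. No separate table for the sensitivity analysis appears in SAP 10.1.

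**The concern.** A covariate with one value per subject shifts all of that subject's log AUCs by the same amount, so it drops out of the difference between two of his periods. Protocol 1.2.2 ties levodopa concentrations to body weight. A weight effect of that kind, common to all treatments, cancels from a log ratio. Only an effect of weight or age that differs between treatments can alter D/A for heavier or older men, and the model has no such term. Close agreement between the two analyses could then be taken as evidence of robustness when it follows almost entirely from the design.

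The Tukey option adds a second problem. If adjusted limits are tabulated, the sensitivity interval for A–D will be visibly wider than the primary one, and a reader could attribute this to weight and age. In the other direction, the primary block as coded gives the five secondary pairs no Tukey adjustment. These data are to support the choice of combination for later studies (Protocol 2.1), so both the robustness statement and the secondary intervals matter.

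**Working it through.** The plan gives no figure for the sensitivity analysis itself. The inputs below come from SAP 6: within-subject SD 0.139 on the log scale, assumed ratio 1.40 (ln 1.40 = 0.336, as stated there), and 14 randomised or 12 evaluable subjects per group. The 80% power in that section does not follow from these inputs (noncentral t with 30 df gives above 99.99%), but nothing here depends on it.

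**1. Cancellation.** For subject i in a period p under treatment k,

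y = μ + τ(k) + π(p) + β·weight(i) + γ·age(i) + s(i) + e.

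The within-subject difference D − A is τ(D) − τ(A), plus a period difference, plus a difference of residuals; β, γ and s(i) are gone. If every subject has all four treatments and all four periods, the treatment and period terms are orthogonal to anything constant within a subject. The estimated contrast is then the same with or without the covariates. That 14 is not a multiple of the four sequences does not matter. The SE is also the same, provided that the estimated subject variance is positive.

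**2. Size of the shift when periods are missing.** Both SAP models were fitted by REML to 300 simulated groups of 14 per scenario, using the Group 1 example sequences of Protocol Table 2. The documents do not give the following, so they are assumptions: between-subject SD 0.25, log-AUC slopes of −0.012 per kg and 0.003 per year, and the number of lost periods.

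| Scenario | Mean absolute change in log(D/A) | Largest change in the ratio |
|---|---|---|
| Complete data | 0 (at most 5e-16) | 0.0% |
| 2 random periods lost | 0.0009 | 0.6% |
| 5 random periods lost | 0.0017 | 1.7% |
| D lost in the 2 lightest subjects | 0.0026 | 1.0% |
| D lost in the 4 lightest subjects | 0.0047 | 1.7% |
| 2 dropouts | 0.0015 | 1.4% |
| 4 dropouts | 0.0023 | 1.4% |
| Stress: D lost in the 4 lightest, between-subject SD 0.10, slope −0.02 per kg | 0.0115 | 4.7% |

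The SE of the contrast changed by at most 3.7% outside the stress case, where it changed by up to 5.5%. With a true subject variance of zero and complete data, the estimate was unchanged but the SE moved by up to 4%. The SE of the D least-squares mean did change, to about 0.92 times the primary value with complete data.

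**3. Tukey.** The error df are 3(N − 1) − 3, and the SE of A–D is 0.139 × √(2/N). The unadjusted multiplier is t(0.95; df), and the Tukey multiplier for four treatments is q(0.90; 4, df)/√2.

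- N = 14, df 36: SE = 0.139 × √(2/14) = 0.0525. Multipliers are 1.688 and 2.376, ratio 1.41. Half-widths are 0.0887 and 0.1249. At a ratio of 1.40 the 90% interval is 1.28–1.53 unadjusted and 1.24–1.59 with Tukey.
- N = 12, df 30: SE = 0.139 × √(2/12) = 0.0567. Multipliers are 1.697 and 2.394, ratio 1.41. The intervals are 1.27–1.54 and 1.22–1.60.

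An unadjusted p of 0.10 becomes a Tukey p of about 0.34. Significance at 10% after Tukey needs an unadjusted p of about 0.023.

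**4. What an interaction could show.** With 14 complete subjects, the SE of the change in log(D/A) per one SD of weight is about 0.139 × √2 / √13 = 0.0545. Fitting treatment-by-weight and treatment-by-age terms costs 3 df each, which leaves 36 − 6 = 30 df. The 90% half-width is then 1.697 × 0.0545 = 0.093, a factor of about 1.10 in the ratio per SD of weight. Correlation between weight and age would widen this.

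**The case against.** A reader might infer that the covariates cannot change the primary result at all. The documents do not support that. SAP 7.1 removes whole periods from the PP analysis of whole-day parameters after emesis (unless it occurs at 14 h or later), so a PP subject can contribute fewer than four periods. SAP 7.1 also plans an mITT analysis of the primary variable, which includes dropouts, and SAP 7.2.2 handles missing data through the random subject effect. The contrast can therefore move, though only slightly.

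A reader might also infer that any visible difference between the two analyses must be a Tukey artefact. That goes too far: the least-squares means have different SEs in the two models. PROC MIXED also gives unadjusted limits beside the adjusted ones, so the unadjusted A–D interval remains in the output. The misleading comparison arises only if the adjusted columns are tabulated for A–D, and the SAP does not say which columns are. Tukey in that line has a basis, since five of the six pairs are secondary. What remains is that the SAP nowhere exempts A–D in that block, and that the same five pairs have no Tukey in the primary block.

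Nor is this the only check on the primary result: mITT is reported alongside PP, and outlier analyses are possible (SAP 7.2.2 and 7.2.10). It is the only covariate-adjusted one.

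Finally, interactions answer a different question from adjustment, and the protocol commits to adjustment. That objection stands against replacing the main effects, but not against supplementing them.

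**Conclusion.** The point holds in this limited form. The covariate main effects leave the A–D contrast unchanged with complete data and shift it by at most about 1–2% of the ratio when a few periods are missing. Those shifts rest on assumed between-subject variance, covariate slopes and missing-data patterns; a deliberately unfavourable combination reached 4.7%. Kenward–Roger df were not emulated. The Tukey mismatch is an inconsistency between the code and SAP 7.2.6 in both blocks, and its effect on an adjusted A–D interval (41% wider) is much larger than any effect of the covariates on the contrast.

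Nothing here suggests that the primary A–D result is wrong: its code is unadjusted, as 7.2.6 intends, and at the assumed ratio of 1.40 both intervals exclude 1. This is a minor point of interpretation and code consistency.

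**What to change.** - Use the same LSMEANS request in both blocks, for example "lsmeans trtpcd / diff cl alpha=0.10 adjust=tukey ADJDFE=ROW", and state in SAP 8.4.1 that A–D is tabulated with the unadjusted 90% limits and p-value and the other five pairs with the Tukey-adjusted ones. Name the output columns, and mark in Table 14.2.1.3.2 which rows are adjusted.
- Keep the weight and age main effects, as Protocol 8.4.3 commits. Add a sentence that they are expected to change A–D little or not at all, so that agreement is not presented as evidence of robustness.
- As a descriptive supplement, add treatment-by-weight and treatment-by-age terms and report the D/A ratio at low, median and high weight, with those points defined in advance. Record the addition in SAP 8.7.

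The cost is a few lines of SAP text and code plus one more table. The downside is that the interactions are imprecise with 14 subjects per group and should not be used for formal inference.
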